19.0 Confidentiality of data

19.1 Confidentiality of participant records

The Kirby Institute has a personal data confidentiality policy and procedure. Identifying data, when collected is stored on a password protected secure network and only authorised members of the project team will have access to the data. Participant confidentiality will be maintained at all times. In this study identifying data will be collected and used as follows:

Participants will have their full name, phone number and/or email address collected by the site staff and sent to the sponsor via an electronic case report form. These contact details will be used for the purpose of study related notifications only (for example, HCV results notifications and upcoming study visit reminders). The name and phone number and/or email address of up to 3 secondary contacts will be collected in case the study team cannot reach the study participant directly. These contact details will not be used for any other purposes. No other identifying information will be collected.

It may be necessary for the sponsor's representatives, the IRB and regulatory authority representatives to have direct access to the participant's medical records. If study documents need to be photocopied during the process of verifying case report form data, the participant will be identified by a unique code only; full names and other identifying information will be masked.

19.2 Confidentiality of study data

By signing the Clinical Trial Agreement, the site Principal Investigator affirms to the sponsor that information provided to them by the sponsor will be maintained in confidence and divulged only as necessary to the ethics committee and institution employees directly involved in the study. Both ethics committee members and employees must also understand the confidentiality requirements for any information divulged to them. The data generated by this study will be considered confidential, except where it is included in a publication as agreed in the publication policy of this protocol.

At sites where regulations restrict the collection of full date of birth and/or participant initials, the following conventions will be used:

- Date of birth will be entered as 01/01/YYYY
- Initials will be entered as AA-AA, BB-BB, CC-CC etc.

20.0 Governance

This national research protocol is funded by a NHMRC Partnership Grant, Gilead Sciences, Maridulu Budyari Gumal Sydney Partnership for Health, Education, Research and Enterprise (SPHERE), and South Western Sydney Local Health District.

The GeneXpert device and cartridges have been provided by Cepheid. The study is sponsored by the UNSW Sydney and coordinated through the Kirby Institute for Infection and Immunity in Society. The Kirby Institute has established governance and implementation structures which use resources efficiently to deliver program objectives on schedule.

21.0 Financing and insurance

Enrolled participants will receive reimbursement for their study visits to compensate for the time involved.

Financing and insurance details (e.g. indemnity cover, during the course of the study, and compensation in the event of study-related injury) are described in the Clinical Trial Research Agreement between the Site and Sponsor.

22.0 Quality Control (QC) and Quality Assurance (QA)

By signing this protocol, the sponsor agrees to be responsible for implementing and maintaining quality control and quality assurance systems with written standard operating procedures to ensure the study is conducted and data are generated, documented and reported in compliance with the

protocol, Good Clinical Practice standards and all applicable local laws and regulations relating to the conduct of a clinical trial.

As part of quality assurance, authorised staff from Cepheid may visit participating sites to perform installation, maintenance, training or other QA activities on the Xpert machines. Principal Investigators at participating sites with a GeneXpert on premises, will permit access to the GeneXpert instrument on site if required.

23.0 Publication Policy

The results of this study may be published and presented at scientific meetings. Publication of data derived from this protocol will be governed by the Protocol Steering Committee. All published data will be non-identifiable grouped data and will follow the guidelines set forth by the International Committee of Medical Journal Editors (ICMJE).

25.0 Abbreviations List

Abbreviation/Acronym		Description		
Ab	-	Antibody		
AE	-	Adverse event		
Ag	-	Antigen		
ASHM		Australasian Society for HIV, Viral Hepatitis and Sexual		
ASTIVI		Health Medicine		
CI	-	Chief investigator		
CRF	-	Case report form		
DAA	-	Direct acting antiviral		
DBS	-	Dried blood spot		
DSMB	-	Data safety monitoring board		
EC	-	Ethics committee		
ETR	-	End of treatment		
GEE	-	Generalised estimating equation		
HCV	-	Hepatitis C virus		
HIV	-	Human immunodeficiency virus		
ICC	-	Intraclass correlation coefficient		
IRB	-	Institutional review board		
IVD	-	In vitro diagnostics		
MBS	-	Medicare benefits schedule		
NHMRC	-	National Health and Medical Research Council		
NSP	-	Needle syringe program		
PBS	-	Pharmaceutical benefits scheme		
PWID	-	People who inject drugs		
QA	-	Quality assurance		
QC	-	Quality control		
RAS	-	Resistance associated substitution		
RNA	-	Ribonucleic acid		
SAE	-	Serious adverse event		
SVR	-	Sustained virological response		
TGA	-	Therapeutic Goods Australia		
VL	-	Viral load		
WHO	-	World Health Organisation		

26.0 Appendices

26.1 Evaluation of operator training, quality assurance and quality control program for point-of-care and dried blood spot testing for hepatitis C (HCV) infection.

Title	Evaluation of an operator training, quality assurance, and quality control program for point-of-care and dried blood spot testing for hepatitis C (HCV) infection.
Background ar Rationale	The advent of simple direct-acting antiviral hepatitis C (HCV) therapies with cure rates >95% is one of the greatest medical advances in decades, having led to a reversal in liver-related mortality. In Australia, treatment uptake has declined between 2016 (32,000 treated) and 2019/20 (2019: 11,500; 2020: estimated 8,000). Progress towards HCV elimination has been impeded by COVID-19, affecting the delivery of national and state-based HCV strategies.
	Scale-up of HCV testing and treatment will be required to achieve elimination by 2030. Current diagnostic pathways require multiple visits to a practitioner, reducing the proportion who receive a diagnosis. In Australia, 81% of people have had HCV antibody testing (indicative of exposure), but only 47% have had HCV RNA testing (indicative of active infection and the need for HCV treatment). Mathematical modelling suggests that HCV RNA testing needs to increase by at least 50% annually to achieve elimination in Australia by 2030.
	Dried blood spot testing can enhance HCV testing and linkage to care ^{13,14} . Benefits of dried blood spot testing include: 1) avoiding the need for phlebotomy; 2) enables testing for HCV antibodies (exposure) and RNA (active infection); 3) easy and stable to transport/store; 4) allows testing for other viruses (e.g. HIV) and 5) sample collection can be performed by peers or self-collection ¹¹ . In addition, dried blood spot testing has high sensitivity and specificity for the detection of active HCV ¹⁵ .
	Point-of-care HCV testing has also been demonstrated to increase testing and linkage to care ¹⁴ . As part of a clinical observational study in drug treatment clinics and needle and syringe programs (NSPs), our group led the first evaluation of a finger-stick point-of-care HCV RNA assay ^{16,17} which enabled same-day diagnosis of active infection (HCV RNA) in one hour (sensitivity and specificity, 100%) ¹⁷ . These findings have informed regulatory in vitro diagnostic (IVD) approval submissions in Europe and Australia. The next step is to translate this novel discovery into routine clinical practice. There is an unprecedented opportunity to evaluate whether finger-stick point-of-care HCV RNA testing could be integrated into routine practice to enhance HCV testing and treatment among people who inject drugs (PWID). The Kirby Institute, Flinders University, and St. Vincent's Hospital have a strong track record of implementing point-of-care and dried blood spot testing for sexually transmitted infections (STIs), HCV, and SARS-CoV-2 (COVID-19), thus providing an sound foundation on which to scale-up GeneXpert HCV and dried blood spot testing in Australia.
	One of the most critical aspects in the implementation of new point-of-care and dried blood spot testing programs is the development of a program which includes clinical education, operator training and competency assessment, and appropriate risk and quality management. A standardised training program will be developed through the Kirby Institute, Flinders

University International Centre for point-of-care testing, St. Vincent's Hospital, and the Australasian Society for HIV, Viral Hepatitis and Sexual Health Medicine (ASHM). Flexible training resources will be developed specifically for operator use in the required clinical settings. The training program will be delivered to operators using well established training pathways via remote learning platforms, such as GoToMeeting, website tutorials, and other online resources. The training will include pre-analytical (e.g. specimen collection, cartridge preparation, analytical (e.g. test operation including use of software and middleware) and post-analytical components (results interpretation and recording, waste disposal, and environmental decontamination) required to accurately perform patient tests. The HCV point-of-care testing program will also implement a quality system, consistent with best practice and regulatory standards and based upon successful existing programs currently in place for infectious disease pointof-care testing. This program provides an excellent opportunity to prospectively evaluate the effectiveness of the operator training with regard to knowledge improvement, practical competency and professional conduct for performing point-of-care and dried blood spot testing for HCV infection. This data will be useful in the assessment of training effectiveness across different trainee occupations and will be utilised to improve training processes for scale-up of point-of-care and dried blood spot testing. **Study Objectives** This study aims to address several objectives among people participating in point-of-care and dried blood spot testing for HCV infection clinical education, operator training, external quality assurance, and internal quality control programs, including: 1) To evaluate changes in self-reported knowledge about point-of-care and dried blood spot testing for HCV infection; 2) To evaluate changes in self-reported competency in performing point-of-care and dried blood spot testing for HCV infection; 3) To evaluate the concordance of quality control and external quality assurance testing with the expected results in the program; 4) To evaluate the proportion of operators who participate and complete the quality control and external quality assurance program; 5) To evaluate the proportion of tests with error or invalid results; 6) To evaluate the proportion of error/invalid test with a successful repeat point-of-care test. This study will be conducted at services (either needle and syringe programs Study Setting or health services) in Australia. It is envisaged that each site will consent and train a maximum of 4 participants for participation in an operator training, quality assurance, and quality control programs for point-of-care and dried blood spot testing for HCV infection. **Participant** Depending on the exact number of operators undertaking and completing population training at each site, it is anticipated that 100-150 operators will be enrolled and will participate in an operator training, quality assurance, and quality control program for point-of-care and dried blood spot testing for HCV infection. Participants/operators will consist of nurses, physicians, needle and syringe program staff, peer-support workers, other health workers and other staff who have an interest to be appropriately trained. Eligibility criteria Operators at the service are eligible for inclusion if the following criteria are met: 1) Provide written informed consent 2) >18 years of age 3) Staff member who will be performing point-of-care or dried blood spot testing for HCV infection.

Study design

This is an observational study of people who initiate commence and complete training through this "Operator Training, Quality Assurance, and Quality Control Program" that will be developed in collaboration by Flinders University, The Kirby Institute, UNSW Sydney, St. Vincent's Hospital and the Australian Society for HIV, Viral Hepatitis and Sexual Health Medicine (ASHM).

The Program will consist of online pre-requisite learning modules (developed by ASHM), 2) theoretical operator training (developed by Kirby Institute, Flinders University, and St. Vincent's Hospital); 3) practical operator training and 4) competency assessment using quality assurance/quality control (developed by Kirby Institute, Flinders University, ASHM, and St. Vincent's Hospital).

The online prerequisite learning modules will cover: 1) epidemiology, risk factors, and natural history of HCV infection; 2) the importance of why point-of-care and dried blood spot testing for hepatitis C are needed to enhance linkage to care and treatment uptake; 3) markers of HCV infection and the different types of HCV tests; 4) how samples for HCV testing can be collected and where HCV sample testing may occur; 5) the advantages and disadvantages of different diagnostic tools (point-of-care and dried blood spot) and their availability in Australia.

The Operator Training and Quality Assurance/Quality Control will cover online theoretical training will include: 1) specimen collection, 2) sample preparation, 3) general device overview and use 4) test cartridge preparation, 5) test orders, 6) interpretation and actioning of patient results, 6) internal quality control testing, 7) external quality assurance testing, 8) device maintenance and troubleshooting and 9) result notification. Operators completing theory training will be required to pass an online quiz prior to proceeding to practical competency assessment.

Practical competency assessment of the operator performing a negative and positive quality control test will be observed via teleconferencing. Operators will be deemed competent for a period of 2 years, once satisfactory QC testing has been observed. Operator competency certificates will be issued with a unique operator login.

At enrolment, participants will complete a self-administered, online survey. The survey will collect information on demographic characteristics (age, gender), the type of service at which participants are employed, role in service, personal experience with HCV testing and treatment for HCV (e.g. numbers tested and treated), knowledge of hepatitis C infection, and knowledge of HCV point-of-care testing and dried-blood-spot testing. A 5-point Likert scale will be utilised to measure participants' HCV-related competence in (i) ensuring people at risk for HCV are regularly screened, (ii) interpreting test results and diagnose HCV, (iii) collection of a fingerstick sample, (iv) performing dried blood spot HCV testing, (v) performing point-of-care HCV testing, (vi) operating the GeneXpert machine. Participants graded own competence in the six five categories by selecting either (1) Not at all confident, (2) Slight knowledge, skills or competence, (3) Average

competence amongst peers, (4) Confident and competent, (5) Very confident and competent.

All participants will complete a self-administered, online survey following each stage of the operator training process, including completion of the: online pre-requisite learning modules, theoretical operator training, practical operator training and at 6 months post-training completion; and quality assurance/quality control.

Study Procedures

Study Visit	Screening (Enrolment)	Pre- requisite Learning	Theoretical Training	Practical Training	6-month Post- training Review
Informed consent	Х				
Survey (Screening version)	х				
Survey (Follow-up version)		Х	Х	Х	Х

To evaluate the quality system participation rate and the concordance of quality control and external quality assurance testing with the expected results in the program, data will be collected at defined intervals from the GeneXpert devices, evaluated for concordance with the expected result and recorded on a quality control or quality assurance spreadsheet.

We will use data from the point-of-care connectivity systems to measure the uptake of point-of-care testing, error rates (proportion of point-of-care tests with an error code), invalid rates (proportion of point-of-care tests with an invalid result) and successful re-tests (proportion of errors/invalid, with a successful repeat point-of-care test). These data will be provided back to operators as part of the process for improved performance in a summary feedback report.

Study analysis

The population attending HCV education and training sessions will be characterised using descriptive analyses. The frequency and proportion of each participant who responded to surveys at each stage of the operator training process, including online pre-requisite learning modules, theoretical operator training, practical operator training; and quality assurance/quality control will also be evaluated.

We will evaluate knowledge and self-perceived competency related to HCV management and treatment. Competency scores will be re-categorised into a binomial 0/1 response, where 0 indicates little or no competency and includes: (1) Not at all confident, (2) slight knowledge, skills, or confidence, and (3) Average competence amongst peers, and 1 indicates confidence and competence including responses: (4) Confident and competent, and (5) Very confident and competent. Using a McNemar's test for binomial paired data, we will test for a significant change in competency (from baseline (pretraining) to follow-up (6 months post-training) and significance of this change for self-reported participant ability in (i) ensuring people at risk for HCV are regularly screened, (ii) interpreting test results and diagnose HCV, (iii) collection of a finger-stick sample, (iv) performing dried blood spot HCV

testing, (v) performing point-of-care HCV testing, (vi) operating the GeneXpert device among participants who answered all four surveys. Factors associated with poor self-perceived (little/no competency) will be assessed using logistic regression analyses.

We will also assess if knowledge or self-perceived competence leads to improved practice (e.g. lower proportion with error or invalid test results).

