16.0 Operator Training, Quality Assurance, and Quality Control Program

An Operator Training, Quality Assurance, and Quality Control Program for the point-of-care testing and dried blood spot testing for HCV RNA will be developed in collaboration with the International Centre for Point-of-Care Testing, Flinders University; St. Vincent's Hospital, and the Australasian

Society for HIV, Viral Hepatitis and Sexual Health Medicine (ASHM). The aim of the program is to develop clinical education and operator training with an analytical quality component for the point-of-care testing and dried blood spots in the TEMPO study. The program will involve pre-requisite training, theoretical and practical training, and assessments of operator knowledge and competency in the use of the point-of-care testing and/or dried blood spots in a non-laboratory setting.

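### Operator-training appendix: the two point-of-care competency items are analysed in all survey completers, including eligible operators who may do only dried blood spot testing

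*Protocol*

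**What the plan says.** All references are to the Protocol.

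- **Who is eligible.** Appendix 26.1, Eligibility criteria, admits a "Staff member who will be performing point-of-care or dried blood spot testing for HCV infection". Section 16.0 describes assessment of "competency in the use of the point-of-care testing and/or dried blood spots in a non-laboratory setting".
- **How methods are distributed.** Section 8.1 randomises each cluster to one method and ends with 11 clusters on each. Section 22.0 speaks of "Principal Investigators at participating sites with a GeneXpert on premises", which implies that some sites have no device.
- **What is measured.** Appendix 26.1, Study design, has participants rate six competencies on a five-point scale. These include point-of-care testing (v) and operating the GeneXpert (vi). The scale has no not-applicable option.
- **How it is coded and tested.** Under Study analysis, ratings 1 to 3 become 0, "where 0 indicates little or no competency and includes: (1) Not at all confident", and ratings 4 and 5 become 1. Then: "Using a McNemar's test for binomial paired data, we will test for a significant change in competency", from baseline to six months after training. The set for the six items ends with "v) performing point-of-care HCV testing, (vi) operating the GeneXpert device among participants who answered all four surveys".
- **The regression.** "Factors associated with poor self-perceived (little/no competency) will be assessed using logistic regression analyses". No items, denominator or covariates are given.
- **Size.** "it is anticipated that 100-150 operators will be enrolled", with at most four per site. No power or effect size is stated.

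**The concern.** Items (v) and (vi) ask about a device that an operator at a dried blood spot site may never use in practice. Such an operator can honestly rate 1 to 3 at both time points. The coding then records little or no competency, and the stated analysis set keeps that person in.

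Two outputs are exposed:

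- The proportion competent and its change on items (v) and (vi) become averages over device users and non-users. They no longer say how well training works for those who run the device.
- In a regression of poor competency on these items, testing method could be the strongest predictor. If it is left out, other factors that differ between sites, such as occupation or type of service, can pick up its effect.

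The appendix intends these results to show how training works across occupations and to guide scale-up, so the distinction matters for their use.

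**Working it through.** The appendix states no effect, alpha or power for the operator study, so there is no figure of the plan's to reproduce. The check asks how the stated analysis set behaves when some operators do not use the device.

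**Inputs from the Protocol.** 100 to 150 operators; at most 4 per site; 22 trial sites, 11 per method.

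**Assumptions, not in the Protocol.** Among operators who perform point-of-care testing, 45% move from 0 to 1 and 5% from 1 to 0. Dried blood spot-only operators either do not change, or 20% move up and 5% move down. Their share s is varied over 10%, 25% and 50%.

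**Formulas.** With b operators moving up and c moving down among N, the gain is (b − c)/N and McNemar's statistic is (b − c)²/(b + c).

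**Step 1: gain.** Among point-of-care operators it is 45 − 5 = 40 points. Pooled, it is (1 − s) × 40 if the others do not change, and (1 − s) × 40 + s × 15 if they gain 20 − 5 = 15 points.

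| Share s | Point-of-care operators | Pooled, others unchanged | Pooled, others gain 15 |
|---|---|---|---|
| 10% | 40 | 36 | 37.5 |
| 25% | 40 | 30 | 33.75 |
| 50% | 40 | 20 | 27.5 |

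**Step 2: the test.** Take N = 100 and s = 50%, so 50 point-of-care operators with b = 22.5 and c = 2.5.

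- Restricted: 20²/25 = 16.0.
- Pooled, others unchanged: b and c are the same, so again 16.0. Only the denominator of the gain has changed.
- Pooled, others gain 15 points: b = 32.5, c = 5, giving 27.5²/37.5 = 20.2, larger than the restricted value.

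At N = 150 and s = 50% with no change among the others, both versions give 24.0.

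**Step 3: share scored as poor.** Assume that at follow-up 20% of point-of-care operators and 90% of dried blood spot-only operators score 0. The pooled share is (1 − s) × 20% + s × 90%, which is 27%, 37.5% and 55% at the three values of s, against 20% among point-of-care operators. The odds ratio for method would be (0.90/0.10)/(0.20/0.80) = 36. With 80% instead of 90% it would be (0.80/0.20)/(0.20/0.80) = 16.

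**Step 4: can s be read from the Protocol?** No. The 11/11 split counts trial clusters, not operators. The trial sites can supply at most 22 × 4 = 88 operators, fewer than the planned minimum of 100. Reaching 100 to 150 takes at least 100/4 = 25 to 150/4 = 37.5, so 38, sites. The appendix also opens the study to health services, whose mix of methods is not stated.

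**The case against.** A reader might infer that dried blood spot staff are left untrained on the device by design and then marked as incompetent. The Protocol does not say so. Appendix 26.1, Study design, describes one programme. Its theory part covers the device, cartridges and troubleshooting, and an observed quality control test follows. No separate dried blood spot track appears. The and/or in Section 16.0 leaves a split possible but does not establish one. What remains is narrower: whatever the training, an operator who does not use the device at work may still rate low on it six months later.

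A reader might also infer that pooling weakens the planned test. Step 2 shows that it does not. With no change among the others the statistic is identical, and with some gain it rises. The understatement concerns the proportions and the change.

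The regression's population and covariates are not stated, and a protocol may leave them to the analysis plan. So it cannot be said that the regression is pooled without testing method, only that it would mislead if it were. The McNemar set is different, because the appendix fixes it by survey completion alone.

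The pooled result is also a legitimate answer to a question about everyone in the programme. That stands, but on items (v) and (vi) it does not describe those who use the device.

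Finally, operators cannot be sorted cleanly by site for item (iv). Sections 1.3.1, 1.3.2 and 10.1 have a dried blood spot research sample taken at screening in every arm. There is thus no good reason to restrict that item.

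**Conclusion.** The point holds in a limited form. The appendix fixes the set for items (v) and (vi) without regard to testing method, although its own eligibility rule admits operators who do only dried blood spot testing. If such operators are present and gain less, the reported proportions and change understate the result among device users. A regression of these items without method may then largely reflect site method.

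The size is conditional. The loss is 4, 10 or 20 points from an assumed 40-point gain at assumed shares of 10%, 25% or 50% with no gain among those operators. It is smaller if they gain something and nil if there are none. A share of one half is conceivable within the trial sites but cannot be taken as the figure for the operator study.

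This is a worthwhile, low-cost improvement to an observational staff sub-study. It does not touch the trial's primary or secondary outcomes.

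**What to change.** In Appendix 26.1:

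- **Study analysis, test of change.** Analyse items (v) and (vi) in operators who perform point-of-care testing, or report them stratified by testing method. Keep items (i) to (iv) in all operators.
- **Study analysis, regression.** For items (v) and (vi), use the same restriction, or include testing method as a covariate if all operators are kept.
- **Study design, enrolment survey.** Record whether each operator performs point-of-care testing, dried blood spot testing or both. The survey content listed there does not include this, and site allocation is not a safe substitute.

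The cost is one extra recorded variable, a few lines of wording and a smaller denominator for two items.

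### The operator-training test of change from baseline to 6 months uses two surveys but is limited to operators who answered an unclear set of four, which discards usable pairs

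*Protocol*

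**What the plan says.** The operator-training sub-study in Protocol appendix 26.1 collects surveys at several points. The Study design entry gives the first: "At enrolment, participants will complete a self-administered, online survey". It continues: "All participants will complete a self-administered, online survey following each stage of the operator training process". The points it then lists are the pre-requisite modules, theoretical training, practical training and 6 months after training, and the sentence ends by adding quality assurance/quality control. The Study Procedures table shows one screening survey and four follow-up surveys (pre-requisite, theoretical, practical, 6 months).

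The Study analysis entry recodes each competency rating to 0/1 and says: "Using a McNemar's test for binomial paired data, we will test for a significant change in competency". The two time points are pre-training baseline and 6 months post-training. The test covers six self-rated abilities and is run "among participants who answered all four surveys". The same entry will also describe survey response: "The frequency and proportion of each participant who responded to surveys at each stage of the operator training process". On size, the Participant population entry says "it is anticipated that 100-150 operators will be enrolled".

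**The concern.** McNemar's test for a change between two time points uses one pair of answers per operator. The surveys between baseline and 6 months do not enter it. Making an operator's inclusion depend on those surveys can only remove valid pairs; it can never add one. The condition is survey response, not completion of training, so it does not define a trained population either.

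Three things follow. Precision is lost whenever an intermediate survey is missed. The analysed group may lean towards operators who respond reliably, and the appendix intends these results to inform how training is scaled up. And the analysis set cannot be reproduced from the text, because the number four fits the schedule in more than one way.

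**Working it through.** The appendix gives no power, effect size or response rate for this sub-study, so there is no stated figure to reproduce. What follows shows what the rule can cost under stated assumptions.

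**Which surveys are the four?** Side by side, the text allows at least these readings:
- The four follow-up surveys in the Study Procedures table, with the enrolment survey taken as given. All five tabulated surveys are then required.
- Four surveys counting baseline and 6 months, so two of the three intermediate surveys are required.
- The four stages at which Study analysis will report survey response: pre-requisite, theoretical, practical and quality assurance/quality control. That list contains neither enrolment nor 6 months.

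The first two can be carried through as arithmetic.

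**Inputs**
- N = 100 to 150 operators (Participant population entry).
- Assumed: every operator completes the enrolment survey, and each later survey is answered with probability r, independently.

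**Formulas**
- Usable baseline/6-month pairs: N × r
- Four surveys including baseline and 6 months: N × r³
- Enrolment plus four follow-up surveys: N × r⁴
- Ratio of standard errors: √(usable pairs / analysed pairs)

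**At r = 0.85** (0.85³ = 0.614; 0.85⁴ = 0.522)

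| Set | N = 100 | N = 150 | Standard error ratio |
|---|---|---|---|
| Both needed surveys | 85 | 128 | 1 |
| Four surveys including baseline | 61 | 92 | √(0.85/0.614) = 1.18 |
| Enrolment plus four follow-up | 52 | 78 | √(0.85/0.522) = 1.28 |

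**Share of usable pairs lost for other r** (1 − r² for the four-survey reading, 1 − r³ for the five-survey reading)
- r = 0.95: 10% or 14%
- r = 0.90: 19% or 27%
- r = 0.80: 36% or 49%
- r = 0.70: 51% or 66%

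**Other end of the range.** If the same people miss every later survey, or if non-response is dropout so that anyone who answers at 6 months has answered everything before, no pair is lost.

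**Power, for illustration.** Assume discordant probabilities of 0.25 (improved) and 0.10 (worsened), two-sided α of 0.05, N = 150 and r = 0.80. With d = 0.25 − 0.10 = 0.15 and s = 0.25 + 0.10 = 0.35, power is Φ[(d√n − 1.96√s) / √(s − d²)]:
- n = 120 (all pairs): 80%
- n = 77 (four surveys including baseline): 61%
- n = 61 (enrolment plus four follow-up): 51%

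**Selection, for illustration.** Assume half the operators are engaged (r = 0.95, net improvement 40%) and half less so (r = 0.60, net improvement 20%). The true average is 30%.
- All pairs: (0.95 × 0.40 + 0.60 × 0.20) / (0.95 + 0.60) = 32%
- With 0.95³ and 0.60³ as weights: 36%
- With 0.95⁴ and 0.60⁴ as weights: 37%

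This depends entirely on the assumed link between responding and improving. Without that link there is no bias.

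**The case against.** - **The count may be right.** The table has exactly four follow-up surveys, so a reader who infers that four is simply an error for five goes too far. This stands: the count is unclear, not shown to be wrong. The added mention of quality assurance/quality control could even imply a further survey, so no number can be supplied on the authors' behalf.
- **Independence is doubtful.** The stages run in sequence, and operators must pass a quiz before the practical assessment. If missed surveys mostly reflect dropout, the loss is close to nil. This stands, and it makes the 18% and 28% illustrations rather than estimates.
- **Overstatement of the training gain is not shown.** A reader might infer that the restriction inflates the gain. The document does not support that. Bias needs a relation between answering the intermediate surveys and change in competency, and none is documented. With a 0/1 outcome, engaged operators who already rate themselves confident at baseline cannot improve, so bias could run the other way. The replacement set is also selected, on 6-month response.
- **The plan partly covers this.** Response at each stage will be reported, and the sub-study is described as observing staff who start and finish the programme. Reporting response makes the losses visible but does not recover the pairs, and answering surveys is not the same as finishing training.

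None of this supplies a reason to exclude an operator who has both answers.

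**Conclusion.** The point holds in a limited form. The stated rule drops valid baseline/6-month pairs whenever a required intermediate survey is missed, and the set it defines is ambiguous. The cost ranges from nothing (non-response mainly dropout) to a standard error about 18% or 28% larger, depending on how the four surveys are read, at an assumed independent response of 85%. It is greater if response is lower. Selection of more engaged operators is possible, but its direction and size cannot be established from the document.

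The restriction is written into the protocol, so this corrects a stated rule rather than asking for detail that a statistical analysis plan would normally add. Severity is minor: this is an observational sub-study in an appendix, and neither the randomised comparison nor the trial's primary outcome depends on it.

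**What to change.** In appendix 26.1, Study analysis, replace the restriction with: *among operators who answered both the baseline and the 6-month survey*. Keep the complete-responder set as a sensitivity analysis or for describing trajectories across stages, and state which surveys define it, in agreement with the Study design text and the Study Procedures table. That includes saying whether quality assurance/quality control has a survey of its own.

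A comparison of the baseline characteristics of included and excluded operators would help readers judge selection, since the two-survey set still depends on 6-month response.

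The cost is one phrase and one clarifying sentence. No new data are needed, and the original subset remains available.
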